6. BACKGROUND AND RATIONALE

6.1. Background

Highly active antiretroviral therapy (ART) has changed human immunodeficiency virus (HIV) infection from a fatal illness to a chronic disease [1, 2]. Since the mid-1990's, regimens containing multiple antiretroviral drugs from at least two classes have been the standard of care in HIV treatment [3]. Combination therapy presents multiple barriers to viral replication and limits the development of drug-resistant mutations [3]. Integrase strand transfer inhibitors (INSTI) are the newest tool for prolonging survival and improving quality of life for people with HIV [4]. This class of medications includes raltegravir (RAL), elvitegravir (EVG), dolutegravir (DTG) and bictegravir (BIC). INSTIs appear to result in a more rapid decline in viral load and higher increases in CD4 counts when compared to protease inhibitors (PI) or efavirenz (EFV) based regimens [5-12].

Body composition has been a concern for patients with HIV since the initial manifestations of severe muscle wasting in the pre-ART era [13-16]. However, these concerns have evolved over time as studies have observed increases in weight among people living with HIV since the introduction of ART [17-19]. Lipodystrophy was associated with primarily older ART regimens but is still observed with some regimens containing newer agents including PIs such as darunavir (DRV) or atazanavir (ATV), INSTIs such as RAL, and non-nucleoside reverse transcriptase inhibitors (NNRTI) such as rilpivirine (RPV) [20-23].

Apart from irregular body fat deposition, weight gain was attributed to an improvement in health initially, especially among those severely immunocompromised. More recently, it has been appreciated that obesity and body mass index (BMI) have been increasing in HIV populations over time both before the initiation of ART and after [19]. In a sample of 14,084 patients living with HIV in the North American AIDS Cohort Collaboration on Research and Design (NA-ACCORD), the percentage of patients who were obese at ART initiation increased from 9% to 18% between 1998 and 2010 [17]. In the Swiss HIV Cohort Study, overweight/obesity prevalence increased from 13% in 1990 to 38% in 2012 [24].

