8.1. Study Design

Study objectives will be evaluated through an observational analysis of a clinical cohort utilizing prospectively-collected EMR data obtained from the OPERA Observational Database. Study participants will be identified from the most recent database build available.

Period of subject inclusion:

- 01AUG2013 (DTG-approval)
- 31DEC2017

Period of observation:

- 01AUG2013 (DTG-approval)
- 31DEC2018

Population:

- A diagnosis of HIV-1, a positive HIV-1 Western Blot, or a positive HIV-1 enzymelinked immunosorbent assay (ELISA); and a detectable HIV-1 viral load test
- At least 18 years of age at the index date
- Male or female
- Prescribed one of the following core agents as part of a 3-drug regimen for the first time between 01AUG2013 and 31DEC2017:
 - DTG (Tivicay[®], Triumeq[®])
 - RPV (Edurant[®], Complera[®], Odefsey[®])
 - RAL (Isentress[®], Isentress HD[®])
 - EVG/c (Vitekta[®], Stribild[®], Genvoya[®])
 - DRV (/r/c) (Prezista[®], Prezcobix[®], Symtuza[®])
 - BIC (Biktarvy[®])
- Not exposed to >1 core agent of interest concurrently

Index date: The index date for an eligible patient is defined as the first date of the first regimen of interest ever prescribed to a patient after 01AUG2013.

Baseline period: The 12-month baseline period preceding the index date will be used to assess patient demographic and clinical characteristics. Data from the visit closest to the index date will be used for analysis.

Observation period: Patients will be observed from their index date until 6,12, and 24 months post-initiation of the regimen of interest, with the final study end date on 31DEC2018.

Censoring events: (i) End of follow-up (6,12, or 24 months after core agent initiation), (ii) cessation of continuous clinical activity*, (iii) core agent discontinuation, (iv) pregnancy, (v) death, or (vi) study end (31DEC2018).

* Continuous clinical activity is defined as at least one clinic visit within a 12month period. Patients failing to meet the continuous clinical activity requirement will be censored 12 months after their last contact.

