8.3.3. Study covariates

The following patient demographic and clinical characteristics will be assessed when first entering the healthcare setting at one of the designated clinics or within the 12-month baseline period preceding the index date. Data from the visit closest to the index date will be used for analysis.

Demographic variables

- Age
 - Continuous (years)
 - Categorical:
 - i. 18-25 years old
 - ii. 26-49 years old
 - iii. 50+ years old
- Gender
- Race/ethnicity (Black non-Hispanic, Black Hispanic, non-Black Hispanic, American Indian, Native Hawaiian, Pacific Islander, Asian, White non-Hispanic)
- History of injection drug use (yes/no)
- Marital status (e.g., single, married/domestic partnership, widowed, divorced/separated, unknown)
- Geographic region (i.e., Northeast, Midwest, South, West)
- Payer type (i.e. Medicaid, Medicare, commercial insurance, AIDS drug assistance programs (ADAP)/Ryan White, cash, no payer information available)

Virologic variables

- HIV viral load at baseline
 - Continuous (copies/mL and log₁₀ copies/mL)
 - Categorical (naïve):
 - Low (<10,000 copies/mL)
 - Moderate (≥10,000 to <100,000 copies/mL)
 - High (≥100,000 copies/mL)
 - Missing
 - Categorical (experienced):
 - Undetectable (<50 copies/mL)
 - Suppressed (≥50 to <200 copies/mL)
 - Viremic (≥200 copies/mL)
 - Missing

Immunologic variables

- CD4 cell count at baseline
 - Continuous (cells/μL)
 - Categorical:
 - High (CD4 > 500 cells/μL)
 - Moderately High (CD4 count >350 to ≤500 cells/µL)
 - Moderate (CD4 count >200 to ≤350 cells/µL)
 - Moderately Low (CD4 count >50 to ≤200 cells/µL)
 - Low (CD4 count ≤50 cells/µL)
 - Missing

Clinical variables

- Year of ART initiation
- Length of previous regimen (ART-experienced patients only)
- Time between index and end of follow-up (months)
- AIDS defining illnesses at baseline
- Mortality Risk (VACS Mortality Index)
- Comorbid conditions occurring on or before the index date (including T2DM and thyroid disease)
- HCV and HBV co-infection
- Blood pressure
- Concomitant medications associated with weight gain [31, 32] (these medications will be characterized and considered for inclusion in the statistical adjustment set)
 - Definite:
 - i. Antipsychotics and mood stabilizers
 - chlorpromazine, clozapine, haloperidol, lithium, olanzapine, valproic acid, risperidone, quetiapine
 - ii. Antidepressants
 - phenelzine, tranylcypromine, citalopram, amitriptyline, nortriptyline, mirtazapine, paroxetine

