Adjusted linear regression models will be used to assess the association between core agent and mean changes in BMI at 6, 12, and 24 months. Baseline variables included in the adjusted model will be selected a priori, based on the literature, including baseline age, sex, race/ethnicity, comorbid conditions and concomitant medications associated with weight gain and weight loss [33, 34], as well as change in viral load and CD4 cell count. Factors associated with the exposure and the outcome identified in the descriptive analyses will be considered for inclusion in the adjusted model if the requirements for confounding are met. Inverse probability-of-censoring weights will be used to account for patients who discontinue treatment or are lost to follow-up and constructed using a logistic regression model.

*This analysis will be stratified by baseline BMI categories (underweight, normal weight, overweight, obese).

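### Calendar year of the index date is neither a listed covariate nor in the named adjustment set, so possible calendar-time confounding of the DTG contrasts in BMI change is left uncontrolled

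*Protocol*

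**What the plan says.** **Index date.** Section 8.1 opens inclusion at "01AUG2013 (DTG-approval") and closes it on 31DEC2017. Patients qualify if "Prescribed one of the following core agents as part of a 3-drug regimen for the first time between 01AUG2013 and 31DEC2017". The anchor is set by "The index date for an eligible patient is defined as the first date of the first regimen of interest ever prescribed" after 01AUG2013, so index dates fall in five calendar years.

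**Covariates.** The only calendar variable in section 8.3.3 is "Year of ART initiation". The year in which the core agent of interest was started is not listed.

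**Model.** For the second primary objective, section 8.5.1 states: "Baseline variables included in the adjusted model will be selected a priori, based on the literature, including baseline age, sex, race/ethnicity". The list continues with "comorbid conditions and concomitant medications associated with weight gain and weight loss [33, 34], as well as change in viral load and CD4 cell count". It then allows additions: "Factors associated with the exposure and the outcome identified in the descriptive analyses will be considered for inclusion in the adjusted model", provided the requirements for confounding are met. Earlier in 8.5.1 the baseline descriptive analyses are defined as covering the covariates in 8.3.2 and 8.3.3.

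**Population.** Section 8.2 restricts this objective to ART-experienced patients.

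**Background.** Section 6.1 reports that "obesity and body mass index (BMI) have been increasing in HIV populations over time both before the initiation of ART and after".

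**The concern.** A confounder here is something related both to which agent a patient starts and to the later change in BMI. The protocol gives some reason to suspect index year on each side.

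- *Exposure.* The window opens on the day DTG was approved, and section 7 calls BIC recently approved. Availability, and so choice of agent, can depend on calendar time.
- *Outcome.* The background reports that BMI has been rising in this population over calendar time.

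If both links exist and index year is not in the model, part of any calendar drift in BMI change is credited to the agents. The differences sought are small, so a modest drift could matter, and a large sample does not remove this kind of error. The study is meant to support evaluation of a weight-gain signal for DTG, so bias in either direction would matter.

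**Working it through.** **1. Can index year reach the model by the stated route?**

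- Named set in 8.5.1: age, sex, race/ethnicity, comorbidities, weight-related medications, change in viral load and CD4. No calendar term.
- Additions come from factors seen in the descriptive analyses, which cover the 8.3.2 and 8.3.3 variables. Index year is in neither section, so the screen does not examine it.

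**2. Does a listed variable stand in for it?**

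- Year of ART start: in ART-experienced patients this normally comes before the index year, by a varying interval.
- Year of ART start plus length of previous regimen (also in 8.3.3): together these approximate index year only for patients leaving a first regimen without a gap. With two or more earlier regimens they do not.
- Neither variable is in the named adjustment set.

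**3. Which index dates can reach each time point?** Section 8.5 restricts each analysis to patients followed at least that long, and observation ends 31DEC2018.

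- 12 months: 31DEC2018 − 12 months = 31DEC2017, the end of inclusion. Nobody is cut off by date at 6 or 12 months.
- 24 months: 31DEC2018 − 24 months = 31DEC2016. Starters in 2017 cannot contribute.

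The calendar mix therefore differs between the 12- and 24-month analyses.

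**4. How large could the bias be?** To first order,

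bias = (drift in BMI change per index year) × (difference in mean index year between two agents, given the other covariates).

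The protocol supplies neither input. With assumed ranges, in kg/m²:

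| Drift per year | Gap 0.5 y | Gap 1 y | Gap 1.5 y | Gap 2 y |
|---|---|---|---|---|
| 0 | 0 | 0 | 0 | 0 |
| 0.02 | 0.01 | 0.02 | 0.03 | 0.04 |
| 0.05 | 0.025 | 0.05 | 0.075 | 0.10 |
| 0.10 | 0.05 | 0.10 | 0.15 | 0.20 |

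For scale, section 6.1 cites 12-month mean BMI increases in an ART-experienced cohort of 0.30 (DTG), 0.24 (RAL), 0.23 (EVG), 0.41 (DRV) and 0.06 (RPV). Absolute differences from DTG:

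- RAL: 0.30 − 0.24 = 0.06
- EVG: 0.30 − 0.23 = 0.07
- DRV: 0.41 − 0.30 = 0.11
- RPV: 0.30 − 0.06 = 0.24

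The drift at which bias equals the cited difference is that difference divided by the gap. For a 2-year gap it is 0.03 (RAL), 0.035 (EVG), 0.055 (DRV) and 0.12 (RPV). For a 1-year gap it is 0.06, 0.07, 0.11 and 0.24. The RPV contrast is not matched anywhere in the assumed range: the maximum is 0.20/0.24 = 83% of it.

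**5. Does the sample-size plan argue against adding the term?** Table 2 in 8.5.3 was reproduced first. The test is the F test of 4 exposure terms with 10 further covariates, f² = ρ²/(1 − ρ²), noncentrality N·f², and denominator df N − 15. Alpha of 0.05 is assumed, since the protocol states none. All ten entries match, from 29,832 at ρ = 0.02 to 292 at ρ = 0.20. Adding index year as one linear term (11 covariates) or as four indicators (14 covariates) leaves all ten unchanged. Power for ρ = 0.20 with the 510 underweight patients stays at 0.972. This ignores variance inflation from correlation between agent and year, which the protocol does not quantify.

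**The case against.** **The list is open.** The set is introduced as including certain variables, only the protocol is at hand, and an SAP could add index year. That is true, and nothing here forbids it. But this protocol fixes covariates down to individual drug names, chooses a different calendar year, and defines a screen that does not look at index year. The choice is poorly fixed rather than merely deferred.

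**The cited trend is in level, not change.** This stands in part. A reader might infer that the background names calendar time as a cause of BMI change. It does not: section 6.1 describes a rise in BMI and obesity across populations. The outcome is within-person change, and the model is stratified by baseline BMI category, which absorbs much of a trend in level. A calendar trend in BMI change is plausible, but it is an inference.

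**Evidence of shifting uptake is thin.** This also stands. No counts by agent and year are given. BIC, the one agent described as recently approved, is limited to 6-month outcomes and says nothing about the 12-month contrasts.

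**The censoring weights.** A reader might infer from the 31DEC2016 limit that a strong predictor has been left out of the weights. The text does not support this. The weights address treatment discontinuation and loss to follow-up, no predictors for them are named, and study end is a separate, administrative censoring event that bites only at 24 months. If 2017 starters were put in the 24-month weight model, their probability of completing would be zero and an index-year term would cause separation.

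**Partial coverage.** Year of ART start and length of previous regimen carry some of the information and are open to the screen. That helps for patients leaving a first regimen only. A reader might also suppose that year of ART start is unknown for patients classed as experienced by low viral load alone; the protocol does not say so.

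**Conclusion.** The omission is confirmed by the text: index year is not a listed covariate, is not in the named set, cannot enter through the confounder screen, and has no adequate stand-in among the listed variables for most ART-experienced switchers. It could bias the DTG contrasts.

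The illustrative size is 0 to 0.20 kg/m², resting on an assumed drift of 0 to 0.10 kg/m² per index year and an assumed 0.5 to 2 year gap in mean index date. At moderate values this could equal the cited RAL, EVG and DRV differences from DTG (0.06, 0.07, 0.11), but not the RPV difference (0.24).

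It would go too far to say that the contrasts are biased, or that the bias is as large as the effect sought throughout. Zero drift is compatible with the document, and direction and size cannot be determined from it. The change is still worth making, because the variable is already held and costs little.

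**What to change.** 1. In 8.3.3, add calendar year of the index date. Keep year of ART start as a separate covariate.
2. In 8.5.1, name calendar year of the index date in the a priori adjustment set, or state why it is left out.
3. Consider it in the weight model for discontinuation and loss to follow-up, fitted only among patients whose index date lets the time point be reached by 31DEC2018. For 24 months that means index dates up to 31DEC2016.

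**Cost.** One variable derived from a date already in the data, and one to four degrees of freedom (five calendar years). The Table 2 sample sizes do not change. The real downside is precision: where an agent's start dates overlap little with DTG's, its contrast will have a wider interval.

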6.2. Rationale

Disentangling weight gain due to improved health status from weight gain due to an undesired effect of therapy requires an assessment of a large number of patients who may be progressing toward a stable health status or in whom a stable health status has been achieved and maintained.

Following raised disproportionality analysis (DPA) scores for both DTG and DTG/ABC/3TC detected through the routine pharmacovigilance, clinical trial data, spontaneous case reports, and published studies were reviewed. The cumulative evidence could not rule out an association between DTG exposure and weight gain, leading to a recommendation for a label change indicating weight gain as an uncommon ADR. This analysis, utilizing data from a large real-world population of treated HIV patients, will provide additional information to support the signal evaluation.

7. **RESEARCH QUESTION AND OBJECTIVE(S)**

Primary:

- Among new users of DTG, RPV, RAL, BIC*, EVG/c and DRV(/r/c): To describe BMI categories, weight, lipid levels (e.g. total cholesterol, HDL, LDL, triglycerides), and lipodystrophy at core agent initiation and at 6,12, and 24 months after core agent initiation, stratified by ART- naïve and ARTexperienced.
- Among ART-experienced new users of DTG vs. RPV, RAL, BIC*, EVG/c or DRV (/r/c): To estimate the association between specific core agent initiation and changes in BMI at 6, 12, and 24 months after core agent initiation.

Secondary:

 Among ART-experienced patients who were suppressed at switch (stable switch) to DTG, RPV, RAL, BIC*, EVG/c, or DRV(/r/c): To describe BMI categories, weight, and lipid panels levels (e.g. total cholesterol, HDL, LDL) at core agent initiation, and at 6,12, and 24 months after core agent initiation

*Due to recent approval and more limited potential follow-up, patients taking BIC will be included for 6-month outcomes only.

8. **RESEARCH METHODS**

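### The only adjusted BMI model conditions on what reads as post-initiation change in viral load and CD4, so it gives an association net of treatment response rather than the overall association in objective 2

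*Protocol*

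**What the plan says.** Protocol Section 7 sets the second primary objective for ART-experienced new users of DTG against each comparator: "To estimate the association between specific core agent initiation and changes in BMI at 6, 12, and 24 months after core agent initiation". Nothing in that wording limits the association to the part not explained by virologic or immunologic response.

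Section 8.5.1 gives the model: "Adjusted linear regression models will be used to assess the association between core agent and mean changes in BMI", at 6, 12 and 24 months and stratified by baseline BMI category. It then says: "Baseline variables included in the adjusted model will be selected a priori, based on the literature". The list that follows is open-ended. It names age, sex, race/ethnicity, comorbidities and weight-related medications, and closes with "as well as change in viral load and CD4 cell count".

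Section 8.3.3 defines the two laboratory covariates only as "HIV viral load at baseline" and "CD4 cell count at baseline". No change variable and no interval for one is defined anywhere in the protocol.

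Section 6.1 states: "INSTIs appear to result in a more rapid decline in viral load and higher increases in CD4 counts", the comparison being with PI or EFV based regimens.

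Two other BMI analyses are planned: unadjusted pairwise Wilcoxon tests between agents (Section 8.5.1) and description in the stable-switch subset (Section 8.5.2). Neither is an adjusted model.

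**The concern.** A change in viral load or CD4 is not a baseline variable, so the sentence contradicts its own label. If the change is measured after the agent is started, it may be a consequence of the agent. The background section says as much for INSTIs against PI or EFV regimens.

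Conditioning on a consequence of exposure does two things. It takes out whatever part of the agent's association with BMI runs through response. It can also create bias, because anything that drives both response and weight, such as adherence or intercurrent illness, becomes linked to the agent once response is held fixed.

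At stake is the only adjusted comparison of agents on BMI, in a study that Section 6.2 says will support evaluation of a DTG weight-gain signal.

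**Working it through.** **1. The passages side by side.** Objective 2 asks for an association with no qualifier. The model's covariates are labelled baseline. Two of the named terms are changes, while the covariate section defines only baseline levels of the same two measures. Further covariates may enter only if they qualify as confounders; a consequence of exposure would not ordinarily qualify, yet these two terms enter without that test. Among the five DTG contrasts (RPV, RAL, EVG/c, BIC, DRV), the Section 6.1 statement bears directly on one, DTG versus DRV (INSTI versus PI). RAL, EVG/c and BIC are in the same class as DTG, and that statement does not cover RPV.

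**2. The plan's own figures.** Table 2 was reproduced with the multiple-regression F test: 4 tested degrees of freedom, 4 + 10 = 14 predictors, noncentrality λ = N·ρ²/(1 − ρ²), power 0.80. Two-sided 5% alpha is an assumption, since Section 8.5.3 states none. All ten sample sizes match exactly, from 29832 at ρ = 0.02 to 292 at ρ = 0.20 (λ = 292 × 0.04/0.96 = 12.2). Reducing the predictors from 14 to 10 leaves all ten unchanged. Table 2 therefore does not depend on whether the change terms stay, go or are replaced.

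**3. What conditioning does to the coefficient.** No input for this is in the protocol, so every value here is assumed:
- c = 0.20: BMI difference between agents not acting through response.
- a = 0 to 0.4: effect of the agent on response, in SD.
- b = 0.1 to 0.5: BMI units per SD of response.
- u = 0 or 0.5: loading of one unmeasured shared cause on both response and BMI.

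Overall difference = c + a·b. Difference in the model with the change term = c − a·u². Gap = a·(b + u²).

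| a | b | u | overall | with change term | gap |
|---|---|---|---|---|---|
| 0 | any | any | 0.20 | 0.20 | 0 |
| 0.2 | 0.25 | 0 | 0.25 | 0.20 | 0.05 |
| 0.2 | 0.25 | 0.5 | 0.25 | 0.15 | 0.10 |
| 0.4 | 0.5 | 0 | 0.40 | 0.20 | 0.20 |
| 0.4 | 0.5 | 0.5 | 0.40 | 0.10 | 0.30 |

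A simulation of the last row with 400,000 patients gave 0.398 and 0.098, in line with the formulas.

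**4. Scale.** The cohort of ART-experienced patients in Section 6.1 gives 12-month mean BMI increases of 0.30 (DTG), 0.24 (RAL), 0.23 (EVG), 0.41 (DRV) and 0.06 (RPV). The differences are: DTG − RAL 0.06, DTG − EVG 0.07, DTG − DRV −0.11, DTG − RPV 0.24. A gap of 0 to 0.30 spans that range.

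**5. Direction.** Take the one contrast that Section 6.1 supports, DTG − DRV = −0.11. Assume 25 to 75 cells/µL more CD4 gain on the INSTI and 0.1 to 0.3 kg/m² per 100 cells. The part through CD4 is then 0.25 × 0.1 = 0.025 to 0.75 × 0.3 = 0.225. Removing it gives −0.11 − 0.025 = −0.135 to −0.11 − 0.225 = −0.335. Here adjustment widens the difference; in step 3 it narrows it.

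**The case against.** The strongest defence is that the adjustment is deliberate. Section 6.2 wants to separate weight gain from restored health from an unwanted drug effect, and conditioning on response serves that aim. Objective 2 says association and specifies neither a total nor a direct effect. Part of this stands: the aim is legitimate. But Section 6.2 ties it to which patients are assessed, not to covariates, and no direct-effect target is stated. A reader of objective 2 would expect the overall association.

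Other points stand as limits on the concern:
- That the change is post-initiation, let alone over the outcome interval, is inferred. The protocol gives no interval, and CD4 could even be parsed as a level.
- The background statement is class-level, and most of the studies cited for it are, by title, in treatment-naïve or first-line patients, whereas objective 2 concerns ART-experienced patients. A reader might infer that the protocol says all the core agents differ in response; it does not.
- A reader might take this model for the only inferential result. Unadjusted pairwise tests of BMI change are also planned, so it is only the sole adjusted one.
- A reader might conclude that baseline viral load, CD4 and BMI are excluded. The covariate list is open and BMI category is a stratifier; they are merely not named. A final list can be left to an SAP, but here the protocol itself names the change terms.
- In patients already suppressed at switch, changes may be small. However, the ART-experienced population also includes viremic patients (Section 8.3.3).

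**Conclusion.** The point holds in this form: as written, the sole adjusted BMI model is mislabelled, uses an undefined variable and, on the natural reading, answers a narrower question than objective 2 puts. Its coefficient would be net of virologic and immunologic response, and would not be a clean direct effect if response and weight share unmeasured causes.

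The size is unknown. The 0 to 0.30 kg/m² range rests wholly on assumed inputs; it shows only that a shift as large as the contrasts of interest is possible. It is zero if agents do not differ in response. A reader might infer that the model would understate differences between agents; the documents do not support that, because for DTG versus DRV plausible inputs move the estimate the other way.

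**What to change.** In Section 8.5.1, replace the change terms in the primary adjusted model with baseline log10 viral load, baseline CD4 and, within each BMI stratum, continuous baseline BMI. All three are already collected (Sections 8.3.2 and 8.3.3).

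If separating recovery of health from drug effect is wanted, state it as its own aim and fit the same model in the stable-switch subset that Section 8.2 already defines, where stratum sizes allow. The underweight stratum has only 510 patients before that restriction.

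Keep any change-adjusted model as a labelled sensitivity analysis, with the interval for each change defined and the no-shared-cause assumption stated. It should also say how missing follow-up laboratory values are handled. Section 8.5.1 accepts that not every patient will have them, and the planned weights address only discontinuation and loss to follow-up.

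Cost: revised wording and extra model runs, each version covering up to 3 time points × 4 BMI strata = 12 fits. No new data are needed for the primary model, and Table 2 is unchanged.

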8.5.3. Study size considerations

The sample size required to detect a range of differences in mean BMI with 80% power for the adjusted linear regression looking at the association between specific core agent initiation and continuous BMI has been estimated under the following assumptions [35]:

• Number of predictors:

The exposure of interest is a 5-level categorical variable, which is equivalent to 4 factor variables, thus requiring 4 degrees of freedom. Calculations were performed assuming a total of 10 covariates included in the model in addition to the exposure variables.

• Effect and variability:

Partial correlations ranging from 0.02 to 0.20 were assumed, corresponding to detectable differences in mean BMI ranging from 0.04 to 0.41. The equivalence between partial correlation and difference in mean BMI was calculated as:

$$\rho = \frac{d}{\sqrt{d^2 + 4}}$$

where ρ = partial correlation and d = difference in mean BMI

The sample sizes required to detect effect sizes ranging from ρ =0.02 to ρ =0.20 with 80% power are presented numerically with corresponding differences in mean BMI (Table 2). They are also presented graphically across a range of partial correlations in Figure 2, along with the estimated sample size available in each stratum of baseline BMI in OPERA, based on the following assumption:

[figure not shown]
 Estimated sample size in OPERA, stratified by baseline BMI category: As of August 17, 2018, there were 91,415 HIV+ patients in OPERA, among whom 17,370 were ART-experienced, had a baseline BMI and initiated one of the core agents of interest for the first time between August 01, 2013 and December 31, 2017. Of these, 510 patients were underweight, 6,598 were normal weight, 6,298 were overweight, and 3,964 were obese at baseline.

0 , ,			C .
Power	Correlation Factor	Difference in Mean BMI	Sample Size Required*
0.80	0.02	0.04	29832
0.80	0.04	0.08	7453
0.80	0.06	0.12	3309
0.80	0.08	0.16	1858
0.80	0.10	0.20	1187
0.80	0.12	0.24	822
0.80	0.14	0.28	602
0.80	0.16	0.32	460
0.80	0.18	0.37	362
0.80	0.20	0.41	292

Table 2. Required sample size for the multivariate linear regression of BMI on core agent, by correlation factor and difference in mean BMI, assuming 80% power

*The estimated sample sizes for each BMI stratum are 510 patients classified as underweight; 6,598 classified as normal weight; 6,298 classified as overweight; and 3,964 classified as obese

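### Objective 2 asks for one association in all ART-experienced new users, but the protocol describes only models stratified by baseline BMI, states no overall estimate and does not name baseline BMI as an adjuster

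*Protocol*

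**What the plan says.** The second primary objective (Protocol sections 3 and 7) is "To estimate the association between specific core agent initiation and changes in BMI at 6, 12, and 24 months after core agent initiation", among ART-experienced new users of DTG versus each other agent. It names no BMI groups.

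For this objective section 8.5.1 specifies: "Adjusted linear regression models will be used to assess the association between core agent and mean changes in BMI at 6, 12, and 24 months". A separate asterisked line adds: "This analysis will be stratified by baseline BMI categories (underweight, normal weight, overweight, obese".

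The adjusters are introduced as follows: "Baseline variables included in the adjusted model will be selected a priori, based on the literature, including baseline age, sex, race/ethnicity, comorbid conditions". Concomitant medications and changes in viral load and CD4 count are named after that. A second route is left open: "Factors associated with the exposure and the outcome identified in the descriptive analyses will be considered for inclusion in the adjusted model", provided they meet the requirements for confounding. Baseline BMI is not named here or in the covariate list of 8.3.3. It does appear among the variables described at baseline in 8.5.1.

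Section 8.5.3 gives 17,370 eligible ART-experienced patients with a baseline BMI: "510 patients were underweight, 6,598 were normal weight, 6,298 were overweight, and 3,964 were obese at baseline". The footnote to Table 2 repeats the four stratum sizes, and the text after Figure 2 argues adequacy from the smallest stratum. The total is never set against Table 2.

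**The concern.** The protocol does not say which estimate answers objective 2. With four comparators, three time points and four strata there are 4 × 3 × 4 = 48 DTG contrasts (52 with BIC at 6 months), and none is marked as the main one. The study is meant to inform a signal evaluation for DTG, so it matters whether the answer is an overall difference, a set of stratum differences, or both.

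Two things are at stake. The first is precision: each stratum uses part of the data, and some differences of the size the protocol cites can be seen only when all patients are used.

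The second is comparability within a stratum. The outcome in 8.3.2 is follow-up BMI minus baseline BMI, so baseline BMI is part of the outcome. It still varies inside each category, above all in the open-ended obese group. If agents differ in mean baseline BMI inside a category, part of that difference can carry into the contrast.

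**Working it through.** **1. The plan's own table.** Section 8.5.3 gives 80% power, a five-level exposure (4 degrees of freedom), 10 covariates and partial correlations ρ from 0.02 to 0.20. It states no significance level; 0.05 two-sided is assumed. Take the F test of the exposure block with f² = ρ²/(1 − ρ²), noncentrality N·f², and 4 and N − 15 degrees of freedom. For ρ = 0.20 and N = 292, f² = 0.04/0.96 = 0.0417, the noncentrality is 12.17 and the power is 0.80. All ten rows of Table 2 are reproduced.

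The same method on Table 2's scale gives these smallest detectable differences:

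| Group | N | Detectable d | SE relative to pooled, √(17,370/N) |
|---|---|---|---|
| All | 17,370 | 0.052 | 1.00 |
| Normal | 6,598 | 0.085 | 1.62 |
| Overweight | 6,298 | 0.087 | 1.66 |
| Obese | 3,964 | 0.110 | 2.09 |
| Underweight | 510 | 0.307 | 5.84 |

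The conversion ρ = d/√(d² + 4) puts d in SD units, so d is in kg/m² only if the SD is 1. The SE ratios assume the same residual SD and agent mix in every stratum.

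**2. Detectable contrasts in kg/m².** Section 6.1 reports mean BMI changes from an ART-experienced switch cohort with ± values. These behave as standard errors: for RPV at 6 months, 0.06/0.07 gives p = 0.39, as reported. At 12 months the reported p = 0.51 is compatible once rounding is allowed for. For DTG (n = 225, √225 = 15) the SD of change is 0.08 × 15 = 1.2 at 6 months and 0.10 × 15 = 1.5 at 12 months.

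Assume patients split equally over five agents, no attrition, and the DTG SD in both groups. The detectable difference is then 2.80 × SD × √(2/(N/5)):

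| Group | N/5 | 6 months (SD 1.2) | 12 months (SD 1.5) |
|---|---|---|---|
| Pooled | 3,474 | 0.08 | 0.10 |
| Normal | 1,319.6 | 0.13 | 0.16 |
| Overweight | 1,259.6 | 0.13 | 0.17 |
| Obese | 792.8 | 0.17 | 0.21 |
| Underweight | 102 | 0.47 | 0.59 |

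**3. The cited differences against these limits.** Absolute differences between DTG (0.18 at 6 months, 0.30 at 12 months) and each comparator:

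| Comparator | 6 months | Within reach | 12 months | Within reach |
|---|---|---|---|---|
| RPV | 0.18 − 0.06 = 0.12 | pooled only | 0.30 − 0.06 = 0.24 | pooled; normal, overweight, obese |
| DRV | 0.32 − 0.18 = 0.14 | pooled; normal, overweight | 0.41 − 0.30 = 0.11 | pooled only |
| RAL | 0.18 − 0.17 = 0.01 | no | 0.30 − 0.24 = 0.06 | no |
| EVG | 0.21 − 0.18 = 0.03 | no | 0.30 − 0.23 = 0.07 | no |

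Using each comparator's own SD (its ± value times √n) changes none of these entries. The 6-month RPV contrast is marginal, however: with an RPV SD of 0.07 × √218 = 1.03, the normal-weight limit is 0.122 against a difference of 0.12.

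**4. Baseline BMI within a stratum.** This is an illustration with assumed values. If change falls by 0.02 to 0.10 kg/m² per unit of baseline BMI, and two agents differ by 1 kg/m² in mean baseline BMI inside a category, the contrast shifts by 0.02 to 0.10. The cited 12-month difference between DTG and DRV is 0.11.

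**The case against.** A reader might infer that the protocol rules out an overall model. The text does not say so. A stratified analysis can be reported beside an overall one, and the title of Table 2 speaks of a single regression. What can be said is that no overall estimate is stated. The sizing by stratum points towards stratum-specific models, and so does objective 1, which uses the same term for ART-naïve and ART-experienced patients with no overall analysis mentioned.

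A reader might also infer that baseline BMI is left out of the model. That is not established. The list is open, and the route for further confounders could admit baseline BMI, which is among the variables compared between agents at baseline. It is accurate only to call it not named. The second route is data-driven and offers consideration, not inclusion. No document shows that agents differ in baseline BMI within a category, and the two middle categories are bounded.

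The strongest objection concerns harm. It would be wrong to say that the cited differences are too small for any stratum: the 12-month RPV contrast of 0.24 exceeds the limit in the three strata that hold 16,860 of 17,370 patients (97%). The 5.84-fold SE applies to 2.9% of patients. Nor does stratifying itself lose information. An inverse-variance combination of the four stratum estimates would cost about 0.2% in SE, since √(17,310/17,370) = 0.998. All of this stands. It narrows the point to the missing combination or overall model.

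Finally, an interaction test and its form are commonly left to the SAP, which is not at hand, so their absence is not an error. The protocol itself fixes the model, adjusters, censoring weights and strata, and the estimate that answers a primary objective belongs with them.

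**Conclusion.** The point holds in a limited form. Objective 2 is worded for all ART-experienced new users, while 8.5.1 and 8.5.3 describe and size only stratified models, with no overall estimate stated and baseline BMI not named as an adjuster. Stratifying on a plausible effect modifier is sound and does not defeat the objective. The gain from an overall estimate is real but narrow: two of the eight cited contrasts come within reach only when pooled, two can already be resolved in at least two strata, and four are out of reach either way.

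These counts rest on equal allocation over five agents, no attrition, a two-sided 0.05 level and the cited cohort's SDs. The restriction in 8.5 to patients followed to each time point will reduce every group, so the absolute limits are optimistic. The size of any bias from baseline BMI within a stratum cannot be read from the documents.

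**What to change.** In 8.5.1, for each time point:

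- State one model in all ART-experienced patients, with the planned censoring weights and adjusted for continuous baseline BMI (for example as a spline), as the overall estimate for objective 2.
- Keep the four strata as subgroup estimates, each also adjusted for continuous baseline BMI.
- Say that differences between strata will be judged by an agent-by-baseline-BMI interaction, not by comparing significance across strata. The form of that test may go to the SAP.

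In 8.5.3, set the total of 17,370 against Table 2 beside the four stratum sizes.

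The cost is a few lines of code and one further table on data already held. The downside is that the pooled estimate averages over BMI groups; the retained strata and the interaction cover this.
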